1.2 Study Outcomes

Primary Outcome:

- BSCVA at 6 months

Secondary Outcomes:

- Endothelial cell counts
- Corneal higher-order aberrations as measured by Pentacam
- Interface haze as measured by Pentacam densitometry
- Change in NEI-VFQ *from baseline to 3 months and 12 months*
- Primary graft failure, defined as a lack of graft clearing or need for re-graft within the first 2 months
- Graft rejection, defined as loss of graft clarity due to edema with evidence of inflammation such as anterior chamber cell or keratic precipitates.

Other Outcomes measured:

- Refraction
- Graft thickness as measured by OCT and pachymetry
- Operative times
- Adverse events/Complication rates

1.3 Study Design

Descemets Endothelial Thickness Comparison Trial (DETECT) is a randomized double-masked, two-arm clinical trial. The purpose of this study is to determine differences in visual outcomes between two types of corneal transplant surgeries. There will be 1:1 randomization to one of two treatment groups – 1.) Ultrathin Descemet's Stripping Endothelial Keratoplasty (DSAEK) OR 2.) Descemet's Membrane Endothelial Keratoplasty (DMEK). The enrollment period is 24 months.

2. ORGANIZATION

Oregon Health & Science University (OHSU) along with the University of California San Francisco (UCSF) will jointly execute this clinical trial. OHSU will mainly be responsible for recruitment and enrollment, intervention implementation, and follow-up visits. UCSF will take the lead on all data analysis, writing of study-related materials, and journal publications.

3. PATIENT FLOW

3.1 Study Timeline

The enrollment period will be 24 months. Study participants will be required to have follow-up visits at months 3 (visit window: 2-4 months), 6 (visit window: 5-7 months), 12 (visit window: 10-14 months), and 24 (visit window: 20-28) from the time of surgery. Additional visits may be needed and will be determined by the surgeon/investigator.

3.2 Eligibility Requirements

3.2.1 Study Area

Recruitment of eligible participants will be done at the Casey Eye Institute and Byers Eye Institute. Eligible participants will be screened by the primary surgeon and research staff at OHSU and Stanford. Potential participants will be approached during a standard of care clinical visit in the outpatient practice of the primary investigator at Casey Eye Institute, OHSU. These are patients that need to have corneal surgery whether or not they participate in this study.

3.2.2 Eligibility criteria for study participants

Only those who meet all of the inclusion criteria and none of the exclusion criteria will be enrolled in this study.

Inclusion Criteria:

- Damaged or diseased endothelium from Fuchs or Pseudophakic Bullous Keratopathy
- Good candidates for corneal transplantation for either DMEK or DSAEK
- Willingness and ability to undergo a cornea transplantation
- Willingness to participate in follow-up visits

Exclusion Criteria:

- Participants who are decisionally and/or cognitively impaired
- Participants who are not suitable for the DMEK or DSAEK surgeries
- Prior Endothelial Keratoplasty (EK) or any other ophthalmic surgery except uncomplicated cataract surgery

- Indication for surgery that is not suitable for EK (e.g. keratoconus, stromal dystrophies and scars)
- Presence of a condition that increases the probability for failure (e.g., heavily vascularized cornea, uncontrolled uveitis)
- Other primary endothelial dysfunction conditions including posterior polymorphous corneal dystrophy and congenital hereditary corneal dystrophy
- Aphakia, or anterior chamber IOL in study eye prior to or anticipated during EK
- Planned intraocular lens exchange of an anterior chamber IOL with a posterior chamber IOL in study at time of study EK
- Pre-operative central sub-epithelial or stromal scarring that the investigator believes is visually significant and could impact post-operative stromal clarity assessment
- Peripheral anterior synechiae (iris to angle) in the angle greater than a total of three clock hours
- Hypotony (Intraocular pressure <10mmHg)
- Uncontrolled (defined as intraocular pressure >25mmHg) glaucoma
- Visually significant optic nerve or macular pathology

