4. PROCEDURES

4.1 Masking

All study participants will be masked to their intervention. The refractionist performing the BSCVA will also be masked. Due to the nature of the intervention, the surgeon and technician performing study visit endothelial cell counts and other imaging will not be masked; however, graders will be masked when possible. Eye bank and UCSF study personnel will not be given any identifying information.

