5.2 Possible Side Effects of Study Medications

Prednisolone: eye irritation, swelling, pain, or redness; pressure within the eye; cataract growth; eye infection

Ofloxacin: eye irritation, swelling, pain, or redness

Tropicamide/Phenylephrine: eye irritation, swelling, pain, or redness; Eye dilation may result in temporary blurred vision, light sensitivity, and increased heart rate.

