Descemet's Endothelial Thickness Comparison Trial

Statistical Analysis Plan

Francis I. Proctor Foundation, University of California San Francisco
Casey Eye Institute, Oregon Health & Science University
Byers Eye Institute, Stanford University

Investigators:

[name], PhD¹
[name], PhD*²
[name]*²
[name]*³
[name], COT²
[name], MS¹

*Principal Investigator

¹Casey Eye Institute, Oregon Health & Science University, Portland, Oregon

² Francis I. Proctor Foundation, University of California San Francisco, San Francisco, California

³Byers Eye Institute, Stanford University, Palo Alto, California

DETECT Statistical Analysis Plan

Table of Contents

1. Background	1
2. Sample Size and Randomization.....	1
3. Baseline Characteristics	1
4. Primary Analysis.....	1
5. Secondary Analyses	1
6. Other Data.....	2

1. Background

Descemets Endothelial Thickness Comparison Trial (DETECT) is a randomized, double-masked, two-arm clinical trial. The purpose of this study is to determine which of two types of corneal transplant surgeries has the better visual outcome. Study participant's eyes will be randomized to one of two treatment groups – 1.) Ultrathin Descemet's Stripping Endothelial Keratoplasty (DSAEK) or 2.) Descemet's Membrane Endothelial Keratoplasty (DMEK).

2. Sample Size and Randomization

We anticipate that 25 eyes per arm would provide 80% power to detect a 0.12 logMAR difference (approximately 1.2 Snellen lines), assuming two-tailed alpha, and a standard deviation of best spectacle-corrected visual acuity (BSCVA) at 6 months of 0.12 logMAR (approximately 1.2 Snellen lines) at 6 months. Participant's eyes will be randomized using random block sizes in Microsoft Excel ([name]).

3. Baseline Characteristics

Baseline characteristics between the 2 arms will be compared using Fisher exact test for categorical variables and Wilcoxon rank sum test for continuous variables.

4. Primary Analysis

For the primary study analysis, we will compare BSCVA between the two groups at the 6-month time period (between 5-7 months) using ANCOVA, with baseline BCVA and treatment group as covariates. Statistical significance will be assessed by permutation with a two-sided alpha of 0.05. (If the correlation coefficient between baseline BCVA and 6 month BCVA has magnitude less than 0.1, we will omit the variable entirely, yielding a post-test only analysis).

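### Lens status is left open by the eligibility criteria and absent from the primary ANCOVA, which costs some precision; a bias is possible only if lens decisions come to differ by arm after allocation.

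*Protocol*

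**What the plan says.** **Who can enter (Protocol 3.2.2).** Eligible diagnoses are Fuchs dystrophy, with no condition on the lens, and pseudophakic bullous keratopathy. Earlier cataract surgery is allowed if uncomplicated, and it is not required. The lens exclusions are "Aphakia, or anterior chamber IOL in study eye prior to or anticipated during EK" and a planned exchange of an anterior for a posterior chamber lens at the study operation. Cataract extraction at EK is neither barred nor mentioned. The same list does exclude eyes whose optic nerve or macula limits vision.

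**When allocation happens (Protocol 3.3).** An eye counts as randomized once the eye bank opens its allocation file, which is after enrolment and before surgery. The eye bank assigns tissue before it knows the arm. No comparable step is written for the lens plan. Under Protocol 3.4.1 the abbreviated form for a second eye is due before surgery; the text does not say before allocation.

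**Masking (Protocol 4.1).** Participants and the refractionist are masked, but "the surgeon and technician performing study visit endothelial cell counts and other imaging will not be masked".

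**Lens change in follow-up (Protocol 5.2).** The listed prednisolone effects include "cataract growth; eye infection".

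**Analysis (SAP 4).** BSCVA at 6 months is compared "using ANCOVA, with baseline BCVA and treatment group as covariates". "Statistical significance will be assessed by permutation with a two-sided alpha of 0.05". Baseline acuity is dropped if its correlation with the 6-month value is below 0.1 in magnitude. All randomized eyes are analysed whatever later surgery they have. Neither document gives a lens stratum, covariate, subgroup or sensitivity model.

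**The concern.** The trial reads 6-month BSCVA as an effect of graft type. In a phakic eye, baseline acuity mixes corneal and lens loss. If the lens is removed at EK, the lens part is gone by month 6. If it stays, that part persists and may grow. Two eyes with the same baseline BSCVA can therefore have different expected 6-month values for a reason unrelated to the graft, and a single baseline slope cannot tell them apart.

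Two separate things are at stake:

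- **Precision.** Lens-related variation stays in the error term, and the arms may differ on it by chance.
- **Bias.** If the lens decision came after allocation and depended on the arm, it would be a co-intervention acting directly on the primary endpoint, and no baseline covariate would remove it.

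**Working it through.** **Inputs from the documents.** The SAP (section 2) states that "25 eyes per arm would provide 80% power to detect a 0.12 logMAR difference", with "a standard deviation of best spectacle-corrected visual acuity (BSCVA) at 6 months of 0.12 logMAR". Alpha is 0.05 two-sided (SAP 4) and allocation is 1:1 (Protocol 1.3).

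**Inputs assumed, because the documents give none.** Share of eyes affected p = 0.3 to 0.5. Residual effect on 6-month BSCVA after baseline adjustment d = 0.05 to 0.10 logMAR.

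**1. The plan's own figure.** With difference 0.12, SD 0.12 and 25 per arm, power is 93.4% (t-test) or 94.2% (normal approximation), not 80%. The gap is on the conservative side and is a separate matter. It matters here only because it shows that precision is not critical at the stated SD.

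**2. Precision gained by a lens term.** Take the lens variance as part of the total SD of 0.12. Share of variance = p(1-p)d²/0.12². Ignoring the cost of estimating the term, the interval ratio is √(1-share). Simulated trials of 50 eyes, comparing mean 95% interval widths, include that cost. In the three-level version the affected eyes are split equally over two levels.

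| p | d | share | √(1-share) | binary term | three levels |
|---|---|---|---|---|---|
| 0.3 | 0.05 | 3.6% | 0.982 | 0.99 | 1.00 |
| 0.5 | 0.05 | 4.3% | 0.978 | 0.99 | 1.00 |
| 0.3 | 0.10 | 14.6% | 0.924 | 0.93 | 0.95 |
| 0.5 | 0.10 | 17.4% | 0.909 | 0.92 | 0.93 |

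The realistic gain is about 1-8% with one binary term and about 0-7% with three levels.

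**3. Power if the lens variance comes on top of SD 0.12.** SD = √(0.12² + p(1-p)d²) = 0.122 to 0.130. Power (t-test) is then 92.5% down to 89.2%.

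**4. Chance imbalance.** The 95% range of the between-arm difference in share is ±1.96√(2p(1-p)/25), which is ±25 points at p = 0.3 and ±28 points at p = 0.5. Multiplied by d, the contrast moves by up to 0.013 (0.254 × 0.05) to 0.028 logMAR (0.277 × 0.10). The standard error already reflects this. It is noise that a covariate can reduce.

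**5. Arm-dependent lens decision, hypothetical.** Bias = difference in lens-surgery rates × d. With a 20-point difference, the bias is 0.20 × 0.05 = 0.010 to 0.20 × 0.10 = 0.020 logMAR, or 8-17% of the 0.12 design difference. The standard error is 0.12 × √(2/25) = 0.034, so type I error would rise from 5% to about 6% and 9% respectively. No passage supports a 20-point difference; the figure only sets a scale.

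**The case against.** The case for leaving the plan alone is substantial.

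- **Randomization covers pre-allocation lens status.** It is balanced in expectation, and omitting a prognostic factor or fitting an imperfect slope does not invalidate a permutation test. This stands in full.
- **Combined lens surgery is inferred from silence.** Neither document mentions phakic eyes or cataract extraction at EK. This stands as a limit: the criteria do not exclude them, but nothing says how many are expected.
- **Some lens planning is already done at eligibility.** Both lens exclusions oblige the surgeon to look ahead to intraocular lens work before enrolment, hence before the file is opened. This narrows the gap: what is missing is a step that fixes the whole lens plan before allocation.
- **Steroid-related cataract is not an arm difference by design,** since one medication schedule applies to everyone. This stands.
- **The forms and the manual of procedures are separate** and may already record lens status. This stands too, so the request is to confirm the field. The SAP makes no use of it either way.

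A reader might also infer the opposite extreme: that the primary comparison is biased, or that the unmasked surgeon will settle lens surgery by arm. The documents do not support that. They leave such a decision possible, do not say when the surgeon learns the allocation, and report no such practice. Masked refraction protects the measurement but not the lens decision.

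**Conclusion.** The point holds as a modest gap in the primary analysis, not a flaw that undermines it. The criteria admit lens situations that baseline BSCVA cannot represent when the lens is removed or changes by month 6, and the SAP does nothing further about them. The baseline covariate is also least secure where the lens matters most, because removing a cataract weakens the correlation on which its retention depends.

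The demonstrable cost is precision, and it is small: an interval about 1-8% longer than it need be, compared with a model carrying one binary term. This rests on the assumed 30-50% share, the assumed 0.05-0.10 logMAR effect and a total SD of 0.12. At the low end of the effect the gain is negligible. A bias of 0.01-0.02 logMAR would need an arm difference in lens surgery that nothing in the documents shows. The change is worth making because it is cheap now. Added after unmasking, the adjustment would be post hoc, and a pre-allocation plan cannot be reliably reconstructed later.

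**What to change.** 1. Confirm that the baseline form, and the abbreviated form for a second eye, record lens status and any lens surgery planned with EK, and that both are completed before the eye bank opens the allocation file. Add the field if it is absent.
2. In SAP section 4, pre-specify one binary pre-allocation term (lens surgery planned with EK: yes/no) in the ANCOVA, under the same permutation test.
3. Tabulate planned and performed lens surgery by arm through month 6. This step is essential, because the covariate handles noise only and cannot remove a difference that arises after allocation; the table would reveal one.

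**Cost.** At most one form field, one or two SAP sentences and one table, plus one degree of freedom in about 50 eyes. A three-level version would use two degrees of freedom and gain slightly less. Eligibility and treatment do not change.

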3.3 Randomization

Each study eye will be randomly assigned to the 1) DSAEK or 2) DMEK treatment group. Block randomization will be performed using a computer program (Statistical package R; Version 2.12; R Foundation for Statistical Computing, Vienna, Austria) by the coordinating site.

Once an eye is enrolled in the study, the study coordinator will assign the study participant's eye an ID (alpha-numeric code) and inform the eye bank (Note: The eye bank will assign tissue to the study participant prior to knowing which arm the study participant is assigned to). The eye bank will then sign into the Dropbox account associated with this study, open the "New Patient" folder, and then open the file named with the particular study participant ID.

Once the eye bank has opened the file, the study eye has been assigned a study participant ID and randomized to treatment group; therefore, they will be included in the intention to treat analysis. (Note: See eye bank protocol for full donor tissue procurement and assignment information).

The treatment assignment will not contain identifiable patient information and will be shared using a password that is only known by the eye bank. The eye bank may only open the document for a given study participant and not for past or future study participants. The treatment assignment document should be moved from the "New Patients" folder to the "Old Patients" folder once opened.

3.4 Study Visits

3.4.1 Baseline Visit

During this visit, eligible patients who are enrolling for the first time will be enrolled in the study and will give consent. The baseline patient form will be completed and the NEI-VFQ will also be administered. If a patient includes a second eye in the study, they will complete an abbreviated baseline patient form for that study eye prior to surgery. They will not complete a second NEI-VFQ at the baseline visit for their second eye. Patients will also complete BSCVA, IOP, Pachymetry, and Pentacam tests at baseline.

3.4.2 *Surgery Visit*

The enrolled study participant's eye(s) will undergo either DSAEK or DMEK surgery. If both of a participant's eyes are included in the study, randomization to DSAEK or DMEK will be performed independently for each eye.

3.4.3 *Follow-Up Visits*

The follow-up patient form will be completed at each visit, for each enrolled eye. Data collected for each follow-up visit will include:

3 month follow-up: BSCVA, IOP, pentacam topography and densitometry pachymetry, optical coherence tomography, and endothelial imaging will be performed. The NEI-VFQ form will also be completed

6 month follow-up data: BSCVA, IOP, pentacam topography and densitometry pachymetry, optical coherence tomography, endothelial imaging, and slit-lamp photography will be performed.

12 month follow-up: BSCVA, IOP, pentacam topography and densitometry pachymetry, optical coherence tomography, and endothelial imaging will be performed. The NEI-VFQ form will also be completed

3.4.4 *Final Visit*

During the Month 24 final visit, the final status and follow-up patient forms will be completed. BSCVA, IOP, pentacam topography and densitometry pachymetry, optical coherence tomography, and endothelial imaging will also be performed.

3.5 Adverse Events (AEs)

During each study visit, the subject will be questioned about AEs in a non-leading manner. All AEs, whether observed by the Investigator, elicited by the Investigator, or spontaneously reported by the subject, will be documented in the subject's chart and the adverse event form. Slit lamp photography will also be completed after any adverse event takes place.

All AEs should be followed until they are resolved or until a stable clinical endpoint is reached. Each AE is to be classified by the Investigator as SERIOUS (SAE) or NONSERIOUS (NSAE).

If a SAE occurs, the investigator at OHSU or Stanford must verbally and/or in writing notify OHSU/Stanford or its designee within 24 hours of the occurrence of the SAE.

The initial SAE report must be followed by a written report, signed by the investigator, and received by OHSU/Stanford or its designee via fax within two working days. The investigator must provide written follow-up reports until the SAE or clinically significant AE has resolved or until a stable clinical endpoint is reached. Notification of an SAE or clinically significant AE must also be submitted to the Institutional Review Board (IRB)/Ethics Committee (EC) in accordance with its requirements. All AEs must be reported from the time that the subject provides informed consent through the last study visit.

4. PROCEDURES

4.1 Masking

All study participants will be masked to their intervention. The refractionist performing the BSCVA will also be masked. Due to the nature of the intervention, the surgeon and technician performing study visit endothelial cell counts and other imaging will not be masked; however, graders will be masked when possible. Eye bank and UCSF study personnel will not be given any identifying information.

4.2 Treatment

For each procedure, the tissue will be prepared by either Lions VisionGift or Sightlife. Each participant will undergo surgery only once and will take approximately 1-2 hours. This study requires 6 visits to the clinic over a period of 2 years, there may be additional post-operative visits (above what the study requires) following this surgical procedure.

4.2.1 DSAEK

For DSAEK, tissue grafts will be cut to the right thickness using a microkeratome prepared at the eye bank per standard eye bank protocol (about 60-90 microns thick). A 4 mm corneal incision will be used, with Endosert as the means of inserting the graft, an FDA approved device for this purpose.

4.2.2 DMEK

For DMEK, endothelial grafts will be pre-peeled at the eyebank (70%). In the operating room the remaining 30% will be peeled, and the endothelium will be stained with trypan blue. A 3.5 mm corneal incision will be used and the graft will be inserted with a modified jones tube injector. The tap technique will be used to position the graft.

4.3 Examinations During Follow-up Visits

There will be 4 follow-up visits for this study – Month 3, 6, 12, and 24; all of these visits would be expected in normal post-operative care. During each follow-up appointment, tests will be done on the participant's study eye; these include: BSCVA, intraocular pressure (IOP), corneal thickness using a Pachymeter, manifest refraction, slit lamp and slit lamp photography, endothelial imaging, Pentacam topography and densitometry, and optical coherence tomography (OCT) testing. Dilated retinal exam will be performed at the discretion of the surgeon.

4.4 Study Schedule

Table 1: Study Schedule

	Visit 1 Pre-op	Visit 2 Surgery	Visit 3 Month 3	Visit 4 Month 6	Visit 5 Month 12	Visit 6 Month 24
Forms						
Consent and Authorization form	X					
Baseline form	X					
NEI-VFQ	X (for 1 st eye)				X	
Follow-up form			X	X	X	X
Final form						X
Procedures						
DMEK or DSAEK surgery		X				
Tests						
IOP	X		X	X	X	X
Pachymetry U/S	X		X	X	X	X
Pentacam (densiometry & topography)	X		X	X	X	X
OCT			X	X	X	X
Endothelial imaging			X	X	X	X
Slit Lamp Photography*	A few patients			X		
BSCVA/ETDRS/MRx	X		X	X	X	X
Total visit time	2 hours	2 hours	1 hour	1 hour	1 hour	1 hour

* Slit lamp photography also taken upon an adverse event

5. STUDY MEDICATIONS

5.1 Prednisolone, Ofloxacin, and Tropicamide/Phenylephrine

The following medications will be administered for treatment purposes: Prednisolone, Ofloxacin, and Tropicamide/Phenylephrine.

5.1.1 Treatment schedule for study medications

The following drug schedule will be followed by all participants: Prednisolone and Ofloxacin four times a day post-operation. Standardized protocol will be to continue Ofloxacin for 1 week, then stop. Prednisolone will be taken four times a day for 4 months, then decreased by 1 drop per month until at 1 drop per day. Participants will stay on 1 drop for at least one year. Steroid treatment can be altered at the discretion of the clinician. The aforementioned drugs will be used for FDA approved indications and will not require an IND. All medications will be protected and only appropriate personnel will administer the drugs. Tropicamide/Phenylephrine drops will be used at the screening exam and at postoperative visits when required. They would be used for pre- and postoperative eye monitoring whether participants are involved in the study or not. These drops are not included in the below dosing schedule since they will be utilized on an as needed bases.

Table 2: Dosing schedule for Prednisolone and Ofloxacin

Medication	Day 1-Day 8	Day 9-Month 3	Month 4	Month 5	Month 6- 12
Prednisolone	4 times/day	4 times/day	3 times/day	2 times/day	1 time/day
Ofloxacin	4 times/day				

